5.0 REGISTRATION PROCEDURES

Patients must be registered in the Siteman Cancer Center database within one working day of enrolling physician signing off on patient eligibility.

6.0 PATIENT VISITS

6.1 Visit #1: Preoperative Evaluation with Surgical Oncologist

The surgical oncologists will discuss treatment options with patients during their initial consultation. Patients will be evaluated to determine whether their age, planned surgical procedure, and medical/surgical history meet the inclusion criteria specified in Section 3.1. Patients will also be evaluated to be sure they do not meet any of the exclusion criteria in Section 3.2. Patients meeting all study criteria will be approached about their ability to participate in this research trial.

The relevant Breast-Q Module is routinely administered pre-operatively to obtain baseline quality of life data on all patients being evaluated for breast cancer surgery. There are 3 distinct BREAST Q surveys based on the type of surgery planned. There is a "Breast Conservation Therapy" version, a "Mastectomy Only" version and a "Mastectomy with Reconstruction" version. Each version has surgery specific pre-operative and postoperative modules. All contain several domains that generate a Q-Score (0-100) enabling quantitative and validated comparison between groups for a particular domain (patient overall satisfaction, satisfaction with care, satisfaction with breasts, etc.). It should take 10-15 minutes for this self-administered

questionnaire to be completed.

6.2 Visit #2: MRI Visit

Diagnostic imaging visit with radiology is performed via MRI per standard of care prior to the surgical procedure that removes breast tissue via lumpectomy or mastectomy. The 3D reconstruction can be performed at any time after image acquisition as image data is stored per standard procedure, in the radiology department. The tumor: breast ratio calculation will be rendered from these images for the purposes of this study. It is possible some patients may have already had a MRI prior to enrollment into this study.

6.3 Visit #3: Plastic Surgeon Visit (*Group B Mastectomy + Reconstruction Only*)

The plastic surgeons will discuss reconstructive treatment options with patients. The plastic surgeons may order additional tests and imaging procedures during this evaluation as needed.

The Breast Q Reconstruction + Expectations Module will be administered pre-operatively to obtain baseline quality of life data if it was not completed at visit #1. It should take 10-15 minutes for this self-administered questionnaire to be completed. The Breast Q is given to all patients seeking breast surgery in the clinical practice and is not a research procedure.

6.4 Surgical Intervention (T=0)

Standardized operation techniques will be used in all treatment groups. All surgeries will be performed by surgical oncologists experienced with breast oncology and affiliated with the Siteman Cancer Center at Washington University. All reconstructions will be performed by one of two plastic surgeons who are also experienced with all forms of breast reconstruction (Drs. [name] and [name]).

Operative notes and pathology reports will be collected.

Postoperative management is standard of care for all patients. Postoperative complications and need for re-excision will be recorded and monitored.

6.5 Visits #4 - 5: Post-Operative Visits

All patients will have routine follow up visits after surgery. Timing of follow-up will be variable among the three groups.

- **Group A:** The surgical oncologist will see the BCT group.
 - Post-Lumpectomy 1st Post-op Visit before Radiotherapy (*1-10 weeks after lumpectomy*)
 - Post-Op Breast Q will be administered and routine imaging taken to quantify volume and mammometric parameters

- Post-Lumpectomy Post-op Visit after Radiotherapy (*6- 18 months after radiation or the latest follow-up time point within the duration confines of our study period.*)
 - Post-Op Breast Q will be administered and routine imaging taken to quantify volume and mammometric parameters

Some patients will require no adjuvant chemotherapy following lumpectomy based on their pathology. These patients are typically radiated 4-10 weeks after lumpectomy. Other patients will require chemotherapy after lumpectomy but prior to radiation. Chemotherapy duration can vary depending on selected treatment regimen but can be between 8-18 weeks excluding Herceptin which typically is administered every 6 weeks for 1 year. Patients receive Herceptin during radiation and reconstruction and so the administration of Herceptin does not independently alter any study time points. Patients will not undergo chemotherapy or radiation until after re-excision is performed in cases where there is a positive cancer margin after lumpectomy per standard of care.

[figure not shown]
- **Group B:** Mastectomy with reconstruction patients will be seen in follow up with plastic surgery.
 - Post-mastectomy 1st Post-op Visit before Completion of Reconstruction (*1-10 weeks after mastectomy*)
 - Post-Op Breast Q will be administered and routine imaging taken to quantify volume and mammometric parameters
 - Post-mastectomy Post-op Visit after Final Reconstruction (*3-8months after final reconstructive procedure or the latest follow-up time point within the duration confines of our study period.*)
 - Post-Op Breast Q will be administered and routine imaging taken to quantify volume and mammometric parameters
- **Group C:** The surgical oncologist will see the mastectomy only group.
 - Post-mastectomy 1st Post-op Visit (*1-10 weeks after mastectomy*)
 - Post-Op Breast Q will be administered and routine imaging taken to quantify volume and mammometric parameters
 - Post-mastectomy Post-op Visit (*6- 18 months after mastectomy or the latest follow-up time point within the duration confines of our study period.*)
 - Post-Op Breast Q will be administered and routine imaging taken to quantify volume and mammometric parameters

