6.6 Variable Duration of Study Observation

Some patients may receive neoadjuvant chemotherapy prior to either lumpectomy or mastectomy. Adjuvant chemotherapy may also be required based on pathologic findings. If required, chemotherapy may begin approximately 6 weeks following surgery. Chemotherapy

duration can vary depending on selected agents but can be between 8-18 weeks. Radiotherapy if needed is usually scheduled for 6 weeks after the final chemotherapy and can last approximately 6 weeks. Treatment time may be lengthened for complications. Reconstruction procedures can happen in multiple stages, therefor extending the time to final completion. This variability in adjuvant treatment will affect the timelines for follow-up and will be recorded for study purposes.

Fig. 1. Study Arms and Duration

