8.0 DATA SUBMISSION SCHEDULE

Case Report Form	Submission Schedule
Original Consent Form	Prior to registration
Eligibility Checklist RedCap Enrollment, Visit 1, Visit 2 MRI, and Visit 3 Plastics (if applicable)	Prior to surgery
RedCap Surgical Intervention	Following receipt of final operative and pathology reports
RedCap Follow-Up Forms Post-Operative Visit 1, Oncology Course, and Post-Operative Visit 2	
Group A:
 
 ○ Post-Lumpectomy 1st post-op visit before Radiotherapy (1-10 weeks after lumpectomy) ○ Post-Lumpectomy post-op visit after radiotherapy (6-18 months after radiation or the latest follow-up time point within the duration confines of our study period.) 
Group B:
 
 ○ Post-mastectomy 1st post-op visit before completion of reconstruction (1-10 weeks after mastectomy) ○ Post-mastectomy Post-op Visit after final reconstruction (3-8 months after final reconstructive procedure or the latest follow-up time point within the duration confines of our study period.) 
Group C:
 
 ○ Post-mastectomy 1st post-op visit (1-10 weeks after mastectomy) Post-mastectomy post-op visit (6-18 months after mastectomy or the latest follow-up time point within the

	duration confines of our study period.)
Unanticipated Event via HRPO	At the time of any unanticipated event
MRI T:B ratio, Breast Q-Scores, and Vectra Mammometrics	The coordinators will ensure MRI performed, Breast-Q's completed and Vectra images captured during active patient phase. MRI T:B ratio will be performed late in the active study phase to allow for a limited number of staff to perform bulk of measurements to optimize standardization. There is also a possibility the software will be upgraded to automate the T:B ratio later in the study period. Breast-Q scores and Vectra mammometrics will be also evaluated in bulk late in the active study phase using SAS, SPSS, or another similar statistical program.

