10.3 Study Design

All DCIS, LCIS and Stage IA-IIB breast cancers that are reasonably treated with mastectomy or BCT will be screened for eligibility for participation in this study. There will be significant heterogeneity within each group in terms of presence/absence, type, timing (adjuvant/neoadjuvant) and duration of chemoradiation administered. To standardize the timing of our outcome measurement, t=0 will always be in relation to the tumor surgery (lumpectomy or mastectomy). We will also obtain a late time point for last follow-up at least 6 months after the final intervention whether therapeutic or reconstructive, whichever is last. Data collected at this late time point – relative to the initial cancer resection at t=0 – is expected

to vary substantially (months-year) between subjects. We have carefully selected IIB patients as the most advanced stage of breast cancer included. This enables us to evaluate patients with large (>5 cm) tumors that are candidates for mastectomy or BCT which will be important since it is in the larger tumors we hypothesize that patient satisfaction and mammometric data would favor mastectomy + reconstruction over BCT.

Patients that meet the inclusion criteria but who opt for mastectomy without reconstruction are included as a control group to further evaluate the impact of post-mastectomy reconstruction.

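### For Group A patients who need re-excision, sections 6.5 and 8.0 time Visit 4 from the lumpectomy but Appendix A times it from the margin-clearing surgery, so the pre-radiotherapy measurement may precede the re-excision

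*Combined protocol and SAP*

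**What the plan says.** Three places set the timing of Group A's first post-operative assessment (Visit 4: Breast-Q and 3D imaging).

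- Section 6.5 calls it the "Post-Lumpectomy 1st Post-op Visit before Radiotherapy" and allows 1 to 10 weeks after lumpectomy. It sets no condition on margins.
- Section 8.0 gives the same label and the same window, "1-10 weeks after lumpectomy".
- Appendix A, footnote 5, also allows 1 to 10 weeks, but counts from the lumpectomy that left clear margins. It does not mention radiotherapy.

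Section 10.3 fixes the time origin: "t=0 will always be in relation to the tumor surgery (lumpectomy or mastectomy"; it then describes this as the first removal of the cancer. Section 6.5 treats re-excision for a positive margin as a separate, later event that must come before any chemotherapy or radiation. Neither 6.5 nor 8.0 says where Visit 4 falls relative to it.

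On radiotherapy, section 6.5 says of patients without adjuvant chemotherapy: "These patients are typically radiated 4-10 weeks after lumpectomy". It continues: "Other patients will require chemotherapy after lumpectomy but prior to radiation".

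A secondary objective in section 2.2 asks how radiation affects Q-score, breast volume, nipple position and breast skin surface area in BCT patients. Section 10.5.2 answers it with a before/after comparison within the BCT group and gives no rule for choosing the before record.

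**The concern.** Visit 4 is the only scheduled measurement between surgery and radiotherapy in Group A, so it has to supply the before value for the radiation comparison. That value is meaningful only if surgery on the breast is finished when it is taken.

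Under 6.5 and 8.0, a patient with positive margins can be seen at week 2, be re-excised at week 4 and have a compliant Visit 4. The tissue taken at week 4 then appears as volume lost between Visit 4 and Visit 5, and the analysis in 10.5.2 would attribute it to radiation. Nipple position, skin surface area and Q-score are exposed in the same way. Under Appendix A that visit does not count, and a later one does.

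The plan expects re-excision to happen: it is monitored under 6.4, listed as a complication in 7.1 and 10.2, and documented under Appendix A, footnote 7. Study staff could therefore apply either rule in good faith and produce before values that mean different things in different patients.

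**Working it through.** The plan gives no figure to reproduce. The check compares the windows, in weeks from the first lumpectomy.

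**1. Re-excised patients.** Let re-excision fall at week r. The documents do not give r; I assume 2 to 8.

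- Sections 6.5 and 8.0: weeks 1 to 10, whatever r is.
- Appendix A, footnote 5: weeks r + 1 to r + 10.
- Valid under both: weeks r + 1 to 10.
- Valid under 6.5/8.0 but taken before re-excision: weeks 1 to r.
- Valid under Appendix A only: after week 10, up to week r + 10.

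| r (assumed) | 6.5 and 8.0 | Appendix A | Both | 6.5/8.0, before re-excision | Appendix A only |
|---|---|---|---|---|---|
| 2 | 1-10 | 3-12 | 3-10 | 1-2 | 10-12 |
| 4 | 1-10 | 5-14 | 5-10 | 1-4 | 10-14 |
| 8 | 1-10 | 9-18 | 9-10 | 1-8 | 10-18 |

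A visit in the week just after re-excision (r to r + 1) also fits 6.5/8.0 but not Appendix A. The later the re-excision, the less the rules share. The before-radiotherapy condition of 6.5 and 8.0 applies on top of their window.

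**2. Patients cleared at the first lumpectomy.** Both anchors are the same operation, so both windows are weeks 1 to 10. There is no conflict.

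**3. Radiotherapy.** Without adjuvant chemotherapy, the typical 4-10 week radiation time lies inside the 1-10 week window. Sections 6.5 and 8.0 also require the visit to come before radiotherapy, so the effect is a shorter usable window, as short as weeks 1 to 4. With adjuvant chemotherapy, section 6.6 says "chemotherapy may begin approximately 6 weeks following surgery" and that its "duration can vary depending on selected agents but can be between 8-18 weeks", with radiotherapy usually 6 weeks after the last chemotherapy. Radiotherapy then starts at about 6 + 8 + 6 = 20 to 6 + 18 + 6 = 30 weeks, well clear of week 10.

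**4. Possible size of the volume error.** None of these inputs is in the documents; all are assumed: breast volume 500 mL, re-excision specimen 20-40 mL, 10-30% of Group A re-excised, and every re-excised patient measured before re-excision.

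- Per affected patient: 20/500 = 4% to 40/500 = 8% of breast volume.
- Mean over Group A: 0.10 × 4% = 0.4% to 0.30 × 8% = 2.4%.

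If only half of the re-excised patients were measured too early, the mean shift would halve to 0.2-1.2%. The documents offer no basis for a corresponding figure for Q-score, and no radiation effect or standard deviation for volume to compare it with.

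**The case against.** The strongest reply is that the three texts can be read together. Footnote 5 may only specify which lumpectomy counts, and a visit can often satisfy all three, as the table shows. Re-excision must precede radiation, so an interval after clearance and before radiation exists. Re-excision is recorded, section 6.6 says variation in treatment timing will be recorded, and section 8.0 lists an Oncology Course form, so misplaced records could probably be identified. Two figures, one beneath the Group A text in 6.5 and Fig. 1 in 6.6, are not available here and might show the intended timeline. The comparison at stake is one of six secondary questions.

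Much of this stands, and it limits the point. It does not remove it. Sections 6.5 and 8.0 as worded do not require Visit 4 to follow re-excision, and 10.3 supports counting from the first operation. Section 10.2 names neither a re-excision date nor a radiation start date, and 10.5.2 does not say what to do with a mistimed record. Identifying such a record also does not supply the measurement that was not taken.

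Two stronger readings are tempting and are not supported. First, a reader might infer from the 1-10 and 4-10 week ranges that the schedule allows Visit 4 after radiation has begun, and might turn the overlap into a share of visits. Sections 6.5 and 8.0 both require the visit to come before radiotherapy. Appendix A merely omits the condition, and its table lists discussion of treatment options, radiotherapy included, at that visit. The overlap concerns only patients without adjuvant chemotherapy, the 4-10 weeks is a typical time rather than a stated start date, and a share of calendar weeks is not a share of patients. Second, a reader might infer bias in the primary analysis. Visit 4 appears to supply t=1 in the models of 10.5, but nothing in the documents shows an effect on the group-by-T:B ratio interaction.

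**Conclusion.** The inconsistency is real and confined to Group A patients who need re-excision. For them, 6.5 and 8.0 permit a before-radiotherapy measurement that precedes the final surgery, and Appendix A permits visits after week 10 that 6.5 and 8.0 would reject. The consequence falls mainly on the secondary before/after-radiotherapy comparison, where surgical change could be counted as radiation change.

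Its size cannot be determined from the documents. The 4-8% per affected patient and 0.4-2.4% on average are illustrations resting on the assumed breast volume, specimen size and re-excision rate; the average also assumes that every re-excised patient was seen too early, which makes it an upper reading for those inputs. The omission of the radiotherapy condition from Appendix A is a gap to close, relevant only without adjuvant chemotherapy. It is not evidence that the plan allows measurement during radiation.

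**What to change.** Reconcile sections 6.5, 8.0 and Appendix A, footnote 5, to a single measurement rule: the Group A Visit 4 Breast-Q and 3D image are taken after the last margin-clearing excision (lumpectomy or re-excision), within 1 to 10 weeks of it, and before the first radiation treatment. This concerns only when the assessment is made; treatment and its timing stay as they are.

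Add to section 10.5.2 that a record taken before a re-excision or after the start of radiation is kept in the database but is not used as the pre-radiation value. To apply that rule, the dates of re-excision and of the first radiation treatment need to be available; if the existing forms do not already hold them, name them in section 10.2.

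The cost is wording in three places and a sentence in the analysis section, with no added visit. In re-excised patients the first routine visit would no longer serve as the before value and a later routine visit would be used, so a few pre-radiation values may be missing.

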6.6 Variable Duration of Study Observation

Some patients may receive neoadjuvant chemotherapy prior to either lumpectomy or mastectomy. Adjuvant chemotherapy may also be required based on pathologic findings. If required, chemotherapy may begin approximately 6 weeks following surgery. Chemotherapy

duration can vary depending on selected agents but can be between 8-18 weeks. Radiotherapy if needed is usually scheduled for 6 weeks after the final chemotherapy and can last approximately 6 weeks. Treatment time may be lengthened for complications. Reconstruction procedures can happen in multiple stages, therefor extending the time to final completion. This variability in adjuvant treatment will affect the timelines for follow-up and will be recorded for study purposes.

Fig. 1. Study Arms and Duration

6.7 Criteria for Removal from Study

If the patient, at any time wishes to be removed from the study, they will be. This study does not propose any new interventions – it is an observational study of patients receiving normal, uninfluenced care for the treatment of breast cancer.

6.8 Anticipated Time Duration of Study

RECRUITMENT: 41 Months to recruit

FOLLOW-UP: MONTHS: Variable with minimum 12 months and maximum 4.5 years

TOTAL TIME TO CLOSURE: 58 MONTHS

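### The timing rules for the final Breast-Q conflict, so an early or unfinished result can enter the primary model as the final one

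*Combined protocol and SAP*

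**What the plan says.** Section 6.8 gives three figures for the calendar: "RECRUITMENT: 41 Months to recruit", "FOLLOW-UP: MONTHS: Variable with minimum 12 months and maximum 4.5 years" and "TOTAL TIME TO CLOSURE: 58 MONTHS". It does not say whether follow-up runs from enrolment, screening or surgery.

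Section 6.6 sets out the adjuvant path. "If required, chemotherapy may begin approximately 6 weeks following surgery"; its "duration can vary depending on selected agents but can be between 8-18 weeks"; and "Radiotherapy if needed is usually scheduled for 6 weeks after the final chemotherapy and can last approximately 6 weeks". For lumpectomy patients who need no chemotherapy, section 6.5 says: "These patients are typically radiated 4-10 weeks after lumpectomy".

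Four sets of rules bear on when the last Breast-Q is taken:

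- Section 6.5, section 8.0 and Appendix A: Group A, 6 to 18 months from the end of radiation.
- Section 6.5, section 8.0 and Appendix B (footnote 6): Group B, 3 to 8 months from the last reconstructive procedure.
- The same places and Appendix C, in every arm, Group C included: the window may be replaced, "or the latest follow-up time point within the duration confines of our study period".
- Section 10.3: a late assessment no sooner than 6 months past the last therapeutic or reconstructive step, with no fallback.

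Section 10.5 indexes the Q-score only as t = 0, 1, 2. Its models adjust for a set of patient characteristics, with age, obesity and stage as examples.

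**The concern.** The final Breast-Q is the outcome that carries the treatment comparison, and its definition differs from section to section. The fallback sets no floor: it does not say that radiation or reconstruction must be complete, nor that any interval must have passed. The stated 12-month minimum is shorter than the protocol's own route to Group A's Visit 5 for most of the chemotherapy range that section 6.6 lists. Group B may be assessed at half the interval that section 10.3 requires.

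At stake is what t=2 means in the primary model. The primary objective is the tumor-to-breast ratio at which outcomes favor mastectomy with reconstruction, read from the group-by-ratio interaction in Model 2. If some t=2 scores describe a settled result and others a reconstruction still in progress, and the mix differs by arm, calendar closure becomes part of the arm comparison. Sections 6.6 and 10.3 acknowledge that timing will vary, and 6.6 says the variation will be recorded, but section 10.5 does not say how it will be used.

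**Working it through.** Inputs are from section 6.8 (12 months, 4.5 years, 41 months, 58 months), section 6.6 (6 weeks to chemotherapy, 8 to 18 weeks of it, a 6-week gap, about 6 weeks of radiotherapy), section 6.5 (visit windows; 4 to 10 weeks to radiation without chemotherapy), section 10.3 (6 months) and footnote 2 of the appendices (screening within 90 days of surgery). One month is taken as 4.348 weeks.

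**1. The plan's own minimum.** Closure minus recruitment is 58 − 41 = 17 months, not 12. If the 4.5-year maximum is the first enrollee's, 54 − 41 = 13 months. If the 17 months run from screening and all 90 days are used (90/7 = 12.9 weeks = 3.0 months), 17 − 3.0 = 14.0 months remain after surgery. None of these gives 12.

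**2. Group A with adjuvant chemotherapy.** Surgery to end of radiation is 6 + 8 + 6 + 6 = 26 weeks (6.0 months) to 6 + 18 + 6 + 6 = 36 weeks (8.3 months). Visit 5 opens 6 months later, at 12.0 to 14.3 months, and closes at 24.0 to 26.3 months. The longest chemotherapy that still reaches the opening at 12 months from surgery is 52.2 − 26.1 − 18 = 8.1 weeks.

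**3. Months after radiation at which the last possible Breast-Q falls:**

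| Follow-up available | 8 weeks of chemotherapy | 12 weeks | 18 weeks |
|---|---|---|---|
| 12 months from surgery | 6.0 | 5.1 | 3.7 |
| 12 months from screening, 90 days used | 3.1 | 2.1 | 0.8 |
| 17 months from surgery | 11.0 | 10.1 | 8.7 |
| 17 months from screening, 90 days used | 8.1 | 7.1 | 5.8 |

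**4. Group A without chemotherapy.** With about 6 weeks of radiotherapy, radiation ends at 10 to 16 weeks, so Visit 5 opens at 8.3 to 9.7 months. That fits 12 months counted from surgery.

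**5. Share of Group A that cannot reach the opening.** Assume uniform accrual over 41 months and every patient on the 18-week course (opening at 14.28 months):

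- 12 months from surgery: (14.28 − 12)/41 = 5.6%, about 6%.
- 12 months from screening, 90 days used: (14.28 − 9.04)/41 = 12.8%, about 13%.
- 17 months from surgery: 0.
- 17 months from screening, 90 days used: (14.28 − 14.04)/41 = 0.6%.

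**6. Group B.** With 12 months from surgery, the last reconstructive procedure must be done by month 12 − 3 = 9 under section 6.5, or month 12 − 6 = 6 under section 10.3. Chemotherapy and radiation alone end at 6.0 to 8.3 months. With 17 months the limits are month 14 and month 11. If reconstruction finishes after radiation on the longest path (an assumption), that leaves 14 − 8.3 = 5.7 or 11 − 8.3 = 2.7 months. The documents say only that stages lengthen the time to completion and give no duration, so the share affected cannot be calculated.

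**7. The analysis.** Nothing in section 10.5 names completion of treatment, time since last treatment, or a sensitivity analysis on either.

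**The case against.** The best defense is that the calendar is adequate. The protocol's 41 and 58 months leave the last enrollee 17 months, and nearly every listed Group A path reaches its window in that time. The fallback can also be read mildly: sections 6.5 and 8.0 label the visits as following radiotherapy or final reconstruction, so the added wording may relax only the interval and not the need for completion. It may also serve patients seen later than the window.

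The first part stands for Group A and is why the size there is small. The second leaves an ambiguity: footnote 6 of Appendix B carries no such label, and even on the mild reading no minimum interval remains, against section 10.3.

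A reader might infer three stronger things that the documents do not support.

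- That about 23% of accrual is affected, from (41 − 31.7)/41 with 58 − 26.3 = 31.7. That counts patients who lack the full window on the longest path. Visit 5 is a single visit, so only the opening needs to be reached.
- That Group A's final scores would be taken during radiation. On every listed path radiation ends by week 36, and a score at 12 months from surgery comes 3.7 to 6.0 months later. Delays from complications are mentioned without a figure.
- That the threshold would move by a known amount, for example 3 points if 20% of Group B scored 15 points low. Both inputs would be assumptions. Section 1.2 also separates tumor size from the ratio, stage is among the adjustment variables, and Group A could be scored early too, so the net direction is not established.

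**Conclusion.** The point holds as an inconsistency in the definition and timing of the final outcome. Section 10.3, the Group B window and the fallback cannot all be followed. The 12-month minimum has no start point, disagrees with 58 − 41 = 17, and is too short for Group A's Visit 5 after any adjuvant chemotherapy longer than about 8 weeks followed by radiation.

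For Group A the consequence is minor: 0 to 0.6% of patients if 17 months applies, and 6 to 13% only if 12 months governs and all take the 18-week course, under uniform accrual. The main exposure is staged reconstruction in Group B, where an unfinished result could be coded t=2. Its frequency and its effect on the estimated threshold are unknown from the documents. It is worth correcting because it concerns the primary outcome and the remedy is cheap; it does not show that the comparison is biased.

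**What to change.** 1. Reconcile sections 6.5, 6.8, 8.0 and 10.3 and the visit footnotes in Appendices A to C so that each arm has one minimum interval before the final Breast-Q. For Group B this means settling the 3-month against the 6-month rule; which to keep is for the study team.
2. In section 6.8, state when follow-up starts and restate the minimum so that it agrees with 41 and 58 months. For reference, reaching the Group A opening on every listed path takes about 14.3 months from surgery, or 14.3 + 3.0, about 17.2 months before rounding, from screening with all 90 days used.
3. In section 10.5, code a score as t=2 in the primary model only if radiation (Group A) or final reconstruction (Group B) is complete and the reconciled interval has passed. Define completion so that failed reconstructions are not silently lost, since section 10.2 keeps patients with complications.
4. Keep any other last score as an interim assessment with its recorded time since last treatment. Run a sensitivity analysis that includes these scores, and report their number by arm and tumor-to-breast ratio.

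The cost is wording, one coding rule and one extra analysis, with no added visits or patients. The downside is somewhat fewer t=2 observations among late enrollees. Section 10.5 leaves the choice between a mixed model and GEE open; unweighted GEE needs a stronger assumption about those missing scores, so the choice should be made with this in mind.
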